BIMS	Biobank information management system
EC	Ethical committee
GCP	Good clinical practice
HCC	Hepatocellular carcinoma
ICH	International Council for Harmonization
IRB	Institutional review board
POA	Powers of attorney
PHI	Personal Health Identifiers
SAE	Serious adverse effect
WHO	World Health Organization

SUMMARY

Aspect	Description
Registry title	Establishment of a Tissue Registry for Hepatocellular Carcinoma biopsy specimens for genetic and histologic research (TIR-HCC)
Background	Armenia has one of the highest incidence rates of primary liver cancer in the region according to WHO Globocan initiative.
Objective	To establish a cancer registry to facilitate research and assist in the identification of additional risk factors for hepatocellular carcinoma.
Study Design	Observational study with mixed retro- and prospective data elements.
Participants	Patients of Armenian descent with clinical, biochemical, and imaging evidence of hepatocellular carcinoma.
Data Collection	Tissue and blood samples will undergo histologic and genetic analyses, as well as relevant clinical history, laboratory and imaging results. Gut microbiota profiles will also be sampled. Samples will be collected from 8 institutions in Armenia.
Sample Size	The registry aims to collect data from 500 patients.

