1.2 Compliance Statement

This study will be conducted in full accordance all applicable laws and regulations of the republic of Armenia and with the principles of ICH-GCP. Any episode of noncompliance will be documented.

The investigators will perform the study in accordance with this protocol, will obtain the signed informed consent of the patients and will report unexpected problems in accordance with medical center, Ethical committee (EC) Policies and Procedures and all official requirements. Collection, recording, and reporting of data will be accurate and will ensure the privacy, health, and welfare of research subjects during and after the study.

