3 INVESTIGATIONAL PLAN

3.1 General Schema of Registry/Repository Design

The repository will collect tumor tissue samples, buffy coat/plasma samples, and gut microbiota samples from patients with hepatocellular carcinoma. The patients will be introduced to the registry by assigned multidisciplinary teams from 8 institutions (*see APPENDIX A*):

- Nikomed Medical Center,
- Violeta Medical Center,
- Wigmore Clinic - Medical Center,
- Mikaelyan Institute of Surgery of YSMU,
- Erebouni Medical Center,
- The National Center of Oncology after V.A.Fanarjyan,

TIR-HCC registry protocol – version date: June 6, 2023

-
- Nork Infection Clinic Hospital
 - Keck Hospital of USC

The preliminary storage from the time of collection will be done at the pathologic laboratories HistoGen and Davidyans.

The final destination for tissue specimen storage is Ecosense laboratories in Armenia.

The specimens will be mailed to Institut Pasteur (through tissue mailing systems) for genetic typing, and then mailed back to Armenia for final storage in Ecosense laboratories.

Blood specimens will be stored at the Institute of Molecular Biology “Santé Arménie” Bio-bank in Yerevan, Armenia and undergo the same mailing and return mechanism as the tissue samples.

Gut microbiota samples will be stored in Biological Resource Centre of the Institute of Molecular Biology of Nation Academy of Sciences (NAS), in Yerevan, Armenia, and be profiled upon request from respective investigators and study groups.

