4.2 Biospecimens

4.2.1 Specimen and Collection Procedures for First Specimen

Pathologic identification of the tissue sampled will be done at Histogen and Davidyants laboratories in Yerevan, Armenia. Genetic studies will be carried out at the Pasteur Institute in Paris, France.

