5.3 Biospecimen Collection and Management

Tissue samples will be collected from the operation theater or from the pathology departments of all participating institutions. Identification codes (in a sequential order) will be assigned to the samples, and all further handling will only include the unique identification codes of the patient (decoding available only at the discretion of the biobank director).

The samples will be stored at -80°C or at -30°C if not -80°C is available. Genomic DNA will be subsequently extracted from tissues using the gold standard proteinase K digestion followed by phenol-chloroform extraction and cold ethanol precipitation. Samples will, then, be quantified, and quality controlled. Those suitable for further analysis will be sequenced or genotyped on selected hotspots known to be frequently altered in HCC (TP53, CTNNB1, TERT, AXIN1, ALB, H/K/N-RAS, NFE2L2/KEAP1, FGF19, CDKN2A). Mutations rate and spectra will be determined and correlation with clinical-pathological background will be actively searched through systematic statistical analysis and multidimensional investigation (hierarchical clustering, Bayesian analysis).

Biospecimen collection will take place from plasma and buffy-coats of the patients as well. Extraction of genomic DNA will be conducted similarly to that practiced on liver tissues except that precipitation will take place overnight in a -80°C freezer to ensure a thorough precipitation of small size DNA fragment shed in bloodstream as cell free DNA (cfDNA). DNA will be quantified using Qubit technique and analyzed by droplet digital PCR (DD-PCR) for the presence of TERT -124C>T or TP53 R249S mutations.

The fecal microbiota samples will be stored in cryovials under -80°C conditions in the Biological Resource Centre of the Institute of Molecular Biology of NAS RA.

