5.5.4 Ethic considerations

This protocol will be evaluated by the ethical committee of the Yerevan State Medical University. The Ethics Committee will give its opinion as of whether or not the project correspond to ethical norms and are compliant with respective regulations.

The repository administrations would have the possibility to contact the Ethics Committee for any specific issue encountered during study activities.

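### Does listing Keck Hospital of USC among institutions the Summary places in Armenia leave that site without a workable specimen route?

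*Protocol*

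**What the plan says.** The Summary says of data collection that "Samples will be collected from 8 institutions in Armenia". Section 3.1 also gives eight institutions and names them; the last is "Keck Hospital of USC". Section 3.2.2 attributes the retrospective cases to 7 sites in Armenia.

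On handling, section 3.1 says: "The preliminary storage from the time of collection will be done at the pathologic laboratories HistoGen and Davidyans". Specimens then go to Paris for genetic typing and are "mailed back to Armenia for final storage in Ecosense laboratories". Section 4.2.1 adds: "Pathologic identification of the tissue sampled will be done at Histogen and Davidyants laboratories in Yerevan, Armenia". Section 5.3 names no exception among the sites: "Tissue samples will be collected from the operation theater or from the pathology departments of all participating institutions".

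On governance, section 1.2 says "This study will be conducted in full accordance all applicable laws and regulations of the republic of Armenia", and section 5.5.4 says "This protocol will be evaluated by the ethical committee of the Yerevan State Medical University".

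**The concern.** Read together, these passages seem to assume that every sample originates in Armenia, while the site list includes a hospital that appears to be elsewhere. Tissue removed there could not be in a Yerevan laboratory at the moment of collection, and no inbound shipment is described. The only national law and the only evaluating ethics committee named are Armenian.

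If the site really had no usable route, its specimens could deteriorate before extraction. Because 5.3 sequences only samples that pass quality control, such losses would be concentrated in one site. In the worst case the site would contribute nothing and the other seven would have to make up the number. The ethics committee would also be reading a Summary that misplaces one source of samples.

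**Working it through.** **1. Count the sites.** Section 3.1 lists Nikomed, Violeta, Wigmore, Mikaelyan, Erebouni, the National Center of Oncology, Nork and Keck: 8 entries, so the stated total reproduces. If Keck is abroad, the number in Armenia is 8 − 1 = 7, and the Summary's location phrase is wrong by one site.

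**2. Test the location.** No passage at hand says where Keck is; the inference rests on its name. The 7 sites in section 3.2.2 fit a split of 7 + 1. They fit equally well with eight Armenian sites, one of which had no retrospective cases. Appendix A, which 3.1 cites for the institutions, is not available here and may settle both location and role.

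**3. Test the route.** Set side by side:

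| Apparent obstacle | Text that bears on it |
|---|---|
| First storage at two Yerevan laboratories (3.1 with 4.2.1) | 5.3 collects tissue in operating theatres and hospital pathology departments, so a transfer to those laboratories is implied for every hospital |
| No storage before arrival | 5.3 requires −80°C, or −30°C where −80°C is not available, and names no place for this |
| No cross-border shipment to Yerevan | 3.1 already mails tissue from Armenia to Paris and back; 3.1.1 leaves procedures to each institution's policies |
| Only Armenian law and one committee named | 1.2 also binds investigators to ICH-GCP and to official requirements generally; 5.7 refers to institutional policies for consent |

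Taken strictly, immediate storage at the two laboratories fails for all eight hospitals, so it cannot be the intended meaning. The ordinary reading is that these laboratories hold tissue before final storage at Ecosense. What is left unwritten is one inbound leg and the pathology arrangement for one site.

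**4. Size, if the site delivered nothing.** Inputs: 500 and 220 from 3.2.2 (which also gives 210), and 5 years of inclusion from 3.2.1. The site's share of recruitment is an assumption.

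- Prospective places: 500 − 220 = 280 (500 − 210 = 290 on the other count).
- Equal share: 280 / 8 = 35 patients, and 35 / 500 = 7%.
- Without the eighth site: 280 / 7 = 40 per site. Over 5 years that is 40 / 5 = 8 a year instead of 35 / 5 = 7.

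| Assumed share of 280 | Patients | Part of 500 | Extra recruitment by the other seven |
|---|---|---|---|
| 5% | 14 | 2.8% | 280 / 266 = 1.053, i.e. 5% |
| 12.5% | 35 | 7% | 280 / 245 = 1.143, i.e. 14% |
| 25% | 70 | 14% | 280 / 210 = 1.333, i.e. 33% (here 210 = 280 − 70) |

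These are upper bounds for each share, since they suppose that the site recruits that share and none of it reaches the registry. The 500 is itself an aim in the Summary and a ceiling in 3.2.2. The primary objective in 2.1 is to store information, and the protocol states no hypothesis test, power or precision target that depends on reaching 500.

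**The case for a change.** The best case for a change is that either reading leaves some text wrong. If Keck supplies samples, the Summary is wrong, and 3.1 and 4.2.1 do not cover the site. If it does not, its place in the 3.1 list, the count of 8 and the unqualified wording of 5.3 are wrong. Supply from abroad is plausible, because 3.3.1 requires Armenian descent and not residence in Armenia. Blood and stool samples are also stored in Yerevan under 3.1, so the gap is wider than tissue. Sites and specimen logistics belong in the protocol, not in an analysis plan, and correcting a few phrases would cost little.

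Most of this stands as a description of loose wording. It does not show harm. The temperature rule in 5.3 already covers the interval before arrival, so loss confined to one site is speculation. Naming one evaluating committee excludes no local review, and that committee reads the whole protocol, including the list in 3.1. A possible shortfall depends entirely on assumed shares. An edit would make the text tidier without altering eligibility, sample size, data items or any result.

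**Conclusion.** No change to the plan is called for. If Keck lies outside Armenia, the Summary's location phrase is a clerical slip affecting one of eight sites: 7 in Armenia, not 8, with the total unchanged. The missing shipping and pathology detail for that site is a gap that the sponsor and the operational group would fill in practice, within the storage rule of 5.3 and the local policies admitted by 3.1.1. No stated figure or conclusion of the registry depends on it.

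Two assumptions carry this. The location is inferred from the hospital's name, and Appendix A might confirm or correct it. Any number of patients affected is likewise assumed: 14 to 70 across the shares shown, and 35 at equal shares, even if the site delivered nothing at all.

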1 BACKGROUND INFORMATION AND RATIONALE

1.1 Introduction

According to the most recent epidemiological assessment conducted by the World Health Organization, hepatocellular carcinoma (HCC) emerged as a major threat for public health in Armenia. Indeed, Armenia has one of the highest incidence of primary liver between the Atlantic Ocean and the Chinese border¹. The epidemiological bases of the problem are primarily linked to the spread of hepatitis C virus (HCV) epidemics in the country in the aftermath of the independence from the Soviet Union (September 1991)².

It is well known, however, that liver cancer is a multi-factorial disease that appears in patients submitted sequentially or concomitantly to several risk factors (e.g. hepatitis C virus infection and heavy alcohol intake, or hepatitis B virus infection and aflatoxin B1 intoxication). Moreover, recent publications from the International Cancer Genome Consortium (ICGC) have revealed that hepatitis viruses are not responsible of mutation fingerprints left on tumor genome as it is various chemical compounds rather than infectious agents that trigger mutations³. In Armenia, historical records suggest that chemicals (e.g. chloroprene) may play an active role in the liver tumorigenesis of some patients⁴. However, the spectrum of risk factors is poorly known in Armenia and hence public health measures aiming to prevent HCC development are difficult to implement.

Recent data taught us that the genome of HCC is characterized by a multiplicity of molecular signatures that provide solid clues concerning mutagenic factors involved in disease history from initiation to final progression⁵.

There is scarce data on the pathologic and genetic subtypes as well as gut microbiota profiles of HCC in the Armenian patient population. Most pathologic exams are done for the confirmation of diagnosis, and there is no application of data in clinical or scientific research. Moreover, there is limited data on etiology and epidemiology of liver cancer in Armenia, even though the cancer profile is concerning compared to other similar countries¹. Thus, the establishment of a cancer tissue registry ensures a long term availability of tissue samples for clinical as well as scientific research purposes. In particular, the analysis of molecular changes prevailing in tumors from Armenian patients will, help clinicians and public health stakeholders to identify additional effectors of liver tumorigenesis and to take appropriate measures to reduce the burden of severe liver diseases in the country. The translational data can be used by researchers from other areas to establish relevant clinical and scientific findings.

1.2 Compliance Statement

This study will be conducted in full accordance all applicable laws and regulations of the republic of Armenia and with the principles of ICH-GCP. Any episode of noncompliance will be documented.

The investigators will perform the study in accordance with this protocol, will obtain the signed informed consent of the patients and will report unexpected problems in accordance with medical center, Ethical committee (EC) Policies and Procedures and all official requirements. Collection, recording, and reporting of data will be accurate and will ensure the privacy, health, and welfare of research subjects during and after the study.

2 STUDY OBJECTIVES

2.1 Primary Objective

The primary objective of this study is to provide a mechanism to store the information about subjects with hepatocellular carcinoma.

2.2 Secondary Objectives

Secondary objectives are translational:

- identify the pathologic substance and the main gene targets of mutations (TP53, CTNNB1, TERT) in HCC from Armenian patients
- establish the nucleotide mutation spectrum of these alterations with the ultimate aim to identify what are the mutagenic agents responsible of these changes.
- to determine whether circulating genetic alterations in patients with HCC are suitable for diagnostic, prognostic or follow-up purposes.
- identify presence of specific gut microbiota profiles in patients with HCC

The samples may also be used for research purposes by professionals from multiple specialties, such as surgery, internal medicine/hepatology, genetics.

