3.1.1 Description of the Collecting Sites

Each participating institution based policies will apply for all procedures and workup.

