3.1.2 Overview of the Data/Biospecimen Collection

The specimens will be collected from patients with biopsy-confirmed diagnosis of HCC. Registry organization systems will manage the tissue further. This is be addressed more detailed in section 5.

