3.2 Study Duration, Enrollment and Number of Sites

3.2.1 Duration of Study

The repository will include both retrospective and prospective data. Retrospective data will include post year 2021 cases. The registry will also include prospective patients with new diagnoses of hepatocellular carcinoma, and their tissue samples will be histologically and genetically studied and recorded. Each participant is expected to be followed for 5 years. The duration will encompass the time from the inclusion of the first patient till the end of follow-up of the final patient and is estimated to be around 10 years (5 years of inclusion plus 5 years of follow-up of each patient).

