3.2.2 Total Number of Study Sites/Total Number of Subjects Projected

We have identified 220 retrospective patients diagnosed with hepatocellular carcinoma in 7 investigative sites in Armenia (all patients are post-2021). The majority of the biopsy samples (160 out of 210 or 73%) have been genetically types and histologically studied as well. We have 50 samples that are pending genetic and histologic identification. In addition, we plan to include prospective cases and expand the data range up to 500 patients.

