3.3 Study Population

3.3.1 Inclusion Criteria

- i. Patients with biopsy-confirmed diagnosis of HCC
- ii. Armenian descent
- iii. Having given their signed Informed consent

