4.1.2 Data Elements

- i. Tumor and liver tissue samples resulting from surgical resection
- ii. 10 mL of whole blood collected on EDTA
- iii. Stool samples for further gut microbiota profiling

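### Suitability of circulating alterations for detecting HCC cannot be determined from HCC patients alone, and the prognostic and follow-up aims have no stated blood-draw times or dated observed outcomes

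*Protocol*

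**What the plan says.** Among the translational aims in Protocol Section 2.2 is "to determine whether circulating genetic alterations in patients with HCC are suitable for diagnostic, prognostic or follow-up purposes". The rest of the protocol bears on this as follows.

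- **Who is sampled.** Section 3.1 says that the repository collects, besides tumour tissue, "buffy coat/plasma samples, and gut microbiota samples from patients with hepatocellular carcinoma". Section 3.1.2 states: "The specimens will be collected from patients with biopsy-confirmed diagnosis of HCC". The first inclusion criterion in Section 3.3.1 is "Patients with biopsy-confirmed diagnosis of HCC".
- **What blood is taken, and when.** Section 4.1.2 lists "10 mL of whole blood collected on EDTA" and gives no time or number of draws. Section 5.3 describes DNA extraction and droplet digital PCR for TERT -124C>T or TP53 R249S. Section 5.6 starts procurement after consent in prospective cases. Section 4.2.1 has a heading that mentions a first specimen but describes no later one. Section 3.1.1 adds: "Each participating institution based policies will apply for all procedures and workup".
- **Follow-up and outcome.** Section 3.2.1 says: "Each participant is expected to be followed for 5 years". Appendix B lists history, examination, imaging, tumour and laboratory items. Its only survival entry is an estimate in months, which is not defined.

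**The concern.** The objective promises a judgement on three uses of a blood marker, and each use needs data of a different kind. Detecting a disease needs people without it. Prognosis needs a known sampling time and an observed, dated outcome. Monitoring needs repeated, dated samples. The first is absent from the enrolled population. The other two are not specified in the text.

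As the objective stands, a report that plasma TERT or TP53 mutations are suitable for detecting HCC could rest only on how often they appear in known cases. A prognostic statement could rest on samples drawn at unknown points around resection or other therapy. A monitoring statement would depend on whichever repeat samples happened to exist. Comparators, draw times and outcomes that were never collected cannot be recovered later by analysis.

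**Working it through.** The protocol states no sensitivity, specificity, event count or precision target for this objective, so there is no figure to reproduce. The question is what the described data can identify.

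**1. Diagnostic use, read as detecting HCC**

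- Planned participants: 500 (Summary). Participants without HCC: 0 (Sections 3.1, 3.1.2 and 3.3.1). The Summary describes eligibility in other words, but it too admits only patients with evidence of HCC.
- Detection rate = plasma-positive HCC / all HCC. Both counts are available, so it can be estimated.
- Specificity = plasma-negative non-HCC / all non-HCC = 0/0. It is undefined, and enrolling more HCC patients does not change the denominator.
- Positive predictive value = sens × prev / [sens × prev + (1 − spec) × (1 − prev)]. It needs specificity, so it cannot be estimated for any target population. The negative predictive value fails for the same reason. Within the registry itself prevalence is 1, so the two values are trivially 1 and 0.

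Two items might look like comparators but are not. The Appendix B histology entry allows other tumour types, yet Section 3.3.1 admits only biopsy-confirmed HCC. Liver tissue collected at resection (Section 4.1.2) comes from the same patients and is no control for a blood test.

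**2. Diagnostic use, read as plasma reflecting the tumour**

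Section 5.3 types tumour DNA at hotspots that include TERT and TP53, and tests plasma for one mutation in each. Two proportions can then be estimated: plasma-positive among mutated tumours, and plasma-negative among unmutated tumours. This reading can be answered by the design. Section 2.2 does not say which reading is meant.

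**3. Prognostic use**

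An association with outcome needs a time origin, an event indicator and a date of event or last contact.

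| Needed | Found in the protocol |
|---|---|
| Blood-draw date | Not listed; only after consent in prospective cases (Section 5.6) |
| Treatment or resection date | Therapy is recorded (Section 4.1.1), but dates are not listed |
| Vital status, recurrence or progression, with dates | Not listed in Appendix B |
| Length of observation | 5 years expected (Section 3.2.1), with no outcome named |

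**4. Follow-up use**

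Sections 4.1.2, 4.2.1, 5.3 and 5.6 state no repeat draw and no draw times over the 5 years.

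**5. Number with blood**

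Section 3.2.2 reports: "We have identified 220 retrospective patients diagnosed with hepatocellular carcinoma in 7 investigative sites in Armenia". It goes on to mention biopsy samples only, so it is not stated whether blood exists for these patients. The remaining planned patients number 500 − 220 = 280. The conclusion in step 1 holds whichever number applies.

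**The case against.** The case for leaving the text alone has several parts.

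- *The objective speaks of alterations in patients with HCC, so plasma-tumour agreement may be all that is meant.* This is a fair reading and the design supports it. It stands against saying that every diagnostic aim is out of reach. It does not remove the ambiguity, because suitability for diagnosis is readily taken to mean detecting the disease.
- *The follow-up point rests on silence.* This stands. Procedures are left to institutional policies, one heading hints at later specimens, and the sample-inclusion flowchart (Figure 1) is not visible here. A reader might infer that repeat draws are ruled out, especially from the remark in Section 6.2 that procedures use existing data and specimens. That remark belongs to the adverse-event text and sits awkwardly with prospective procurement in Section 5.6. Only *not specified* can be supported.
- *Appendix B is not presented as the full follow-up dataset.* This also stands. A reader might infer that deaths and recurrences will go unrecorded, or that the survival entry is only a forecast. The text establishes neither: the outcomes are not listed and the entry is undefined. Nor does any section say that samples will be mixed across treatment; they could be.
- *This is a biobank, and later projects need their own ethics approval (Sections 5.1 and 7).* That makes a direct overclaim less likely. The objective is nevertheless stated as one of this study's own.
- *A statistical analysis plan may cover it.* Analysis methods may sit there. Who is enrolled, when blood is drawn and which outcomes are collected are matters for the protocol.

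**Conclusion.** The point holds and should be fixed, with different strength for its parts.

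- **Diagnostic:** firm, on the reading that *diagnostic* means detecting HCC. With 0 of 500 planned participants free of HCC, specificity and predictive values cannot be identified. This is not a matter of precision, and it needs no assumed detection rate. On the concordance reading the design is adequate and only the wording needs to change.
- **Prognostic and follow-up:** a gap in specification. No draw time, repeat draw or dated observed outcome is stated. Prognostic analyses could therefore mix samples from before and after treatment and lack an observed endpoint. It would go too far to say that the protocol excludes serial samples or outcome recording.

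One secondary objective is affected. The primary objective in Section 2.1, a mechanism for storing information, is not.

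**What to change.** **Section 2.2.** Replace the objective with wording such as: *to estimate how often circulating genetic alterations (by ddPCR: TERT -124C>T, TP53 R249S) are detected in patients with HCC and their concordance with the tumour's mutation status, and to explore their association with observed outcome.* Add one sentence: *suitability for detecting HCC, and for monitoring unless dated serial samples are collected, will not be concluded from this registry alone.*

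**Appendix B.** To support the prognostic part, add:

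- the blood-draw date;
- the treatment start or resection date;
- vital status and recurrence or progression, each with its date, or the date of last contact, over the planned 5-year follow-up.

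**Cost.** Two sentences and a few data fields, with no extra patients or blood samples. The stated claim becomes narrower. The fields must be completed over 5 years, and retrospectively for those of the 220 existing cases that have blood. Draw dates and outcomes become harder to recover as the roughly 10-year study proceeds, so the change is cheapest now.
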